4 STUDY DESIGN

4.1 OVERALL DESIGN

This clinical research trial aims to demonstrate the safety of TQ Formula , as well as preliminary efficacy in treatment of Covid-19. The hypothesis is that treatment with TQ Formula will significantly reduce median time to sustained clinical response, defined as a reduction of scores to ≤ 2 on all symptoms of the Modified FLU-PRO Plus, compared with placebo. In addition, it is hypothesized that treatment with TQ formula will significantly reduce viral load and symptom burden from baseline to Day-7 compared to treatment with placebo.

This is a randomized, double-blind, placebo-controlled phase II study to assess the safety and efficacy of TQ Formula versus placebo in the treatment of Covid-19 in an outpatient setting. Participants will be randomized 1:1 to receive either 3 g per day of TQ Formula or placebo (identical in appearance). The participants will receive up to 14 days of dosing.

Screening Visit

The following evaluations should be completed at the Screening visit:

Informed Consent

The purpose and procedures of the study will be fully explained to potential participants. Those wishing to enroll in the study will sign a written informed consent prior to initiating any study related evaluations or procedures.

Demographics

Participant demographics, including age, race and gender will be captured and documented in the source and the electronic case report form (eCRF).

Medical History

Participant medical history, including any surgical procedures, will be captured and documented in the source and the electronic case report form (eCRF).

Inclusion/Exclusion Criteria Evaluation

Participants will be assessed to ensure that they meet all inclusion criteria and do not meet any of the exclusion criteria as listed in sections 5.1 and 5.2

Covid-19 Rapid Test (Antigen)

Participants will be given a CLIA waived rapid antigen Covid-19 test (per site standard procedures) in order to obtain same days results to use for randomization of participants. The test may be performed prior to informed consent as part of standard of care at the clinic.

Concomitant Medication Review

All concomitant medications, including vitamins and supplements, currently being taken by participants will be documented in source and in the eCRF.

Physical Exam

A complete physical exam of the following systems will be performed by the investigator or appropriately qualified designee and documented in the source and in the eCRF at Screen, Day 7 and Day 14. A complete physical examination, performed at screening and other specified visits, should include an evaluation of the head, eyes, ears, nose, and throat, and the cardiovascular, dermatologic, respiratory, gastrointestinal, and neurologic systems. Any abnormality identified at baseline should be recorded in the patient's medical records. Limited, symptom-directed physical examinations should be performed at specified postbaseline visits and as clinically indicated. Changes from baseline abnormalities should be recorded in patient notes. New or worsened clinically significant abnormalities should be recorded as adverse events in the patient's medical records.

Vital Signs

Vital signs, including blood pressure (BP), temperature and heart rate will be collected and documented in source and in the eCRF.

Pulse and Walking Oximetry

SpO2 and 6-minute walk test (walking oximetry) will be performed at screening.

Height and Weight

Height and weight of patient will be taken at screening.

Laboratory Evaluations (Hematology and Serum Chemistry)

Blood samples (approximately 10 ml in total) will be taken for the following laboratory evaluations: Albumin, alkaline phosphatase, total bilirubin, direct bilirubin, bicarbonate, BUN, calcium, chloride, creatinine, glucose, LDH, phosphorus, potassium, total protein, AST, ALT, sodium, CBC/diff, LDH, , CRP, prothrombin time, activated partial prothrombin time, D-dimer

Pregnancy Test

Females of child-bearing potential will have a serum pregnancy test completed.

Baseline Visit

The following evaluations should be completed at the Baseline visit:

Inclusion/Exclusion Criteria Evaluation

Participants will be re-assessed to ensure that they meet all inclusion criteria and do not meet any of the exclusion criteria as listed in sections 5.1 and 5.2

Vital Signs

Vital signs, including blood pressure (BP), temperature and heart rate will be collected and documented in source and in the eCRF.

Sample for quantitative viral load testing (RT-PCR) and confirmation of Covid-19 positive result Participants will have a sample taken for RT-PCR quantitative viral testing.

Serum Collection (Immune monitoring)

Blood samples (approximately 15 ml) will be collected for immune monitoring

Randomization

Participants will be randomized to receive either TQ Formula + Standard of Care (SOC) or placebo +SOC

Administer Study Intervention

Participants will be provided with study treatment kit, with enough capsules for 14 days of treatment, 3 capsules BID.

Concomitant Medications and Adverse Events Review

Participants will be assessed for any new adverse events and any changes in concomitant medications

Patient Reported Outcomes

Participants will receive the Modified FLU-PRO Plus questionnaire to complete on a daily basis for the duration of the study, from randomization to final study visit (Day 21).

Subsequent Study Visits (Including Day 21 Final Visit)

Concomitant Medications and Adverse Events Review

Participants will be assessed for any new adverse events and any changes in concomitant medications at each study visit

Physical Exam

A complete physical exam will be performed by the investigator or appropriately qualified designee and documented in the source and in the eCRF at Day 7 and Day 14. A complete physical examination, performed at screening and other specified visits, should include an evaluation of the head, eyes, ears, nose, and throat, and the cardiovascular, dermatologic, respiratory, gastrointestinal, and neurologic systems. Any abnormality identified at baseline should be recorded in the patient's medical records. Limited, symptom-directed physical examinations should be performed at specified postbaseline visits and as clinically indicated. Changes from baseline abnormalities should be recorded in patient notes. New or worsened clinically significant abnormalities should be recorded as adverse events in the patient's medical records.

Vital Signs

Vital signs, including blood pressure (BP), temperature and heart rate will be collected and documented in source and in the eCRF at each study visit.

Serum Collection (Blood sample for immune monitoring)

Blood samples (approximately 15 ml) will be collected for immune monitoring at Day 7 and Day 14, in addition to the baseline visit.

Sample for quantitative viral load testing (RT-PCR)

Participants will have a sample taken for RT-PCR quantitative viral testing at Day 7 and again at Day 14, in addition to the baseline visit.

Laboratory Evaluations (Hematology and Serum Chemistry)

Blood samples (approximately 10ml in total) will be taken for safety laboratory evaluations (as listed in screening above) at Day 7 and 14 and as clinically indicated at any other study visits

Patient Reported Outcomes

Participants will receive the Modified FLU-PRO Plus questionnaire to complete on a daily basis for the duration of the study, from randomization to final study visit (Day 21).

Safety Follow Up Phone Call (Day 45)

Adverse Events Review

Participants will be called to assess status for any ongoing adverse events and/or serious adverse events

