4.3 JUSTIFICATION FOR DOSE AND FORMULATION

TQ Formula will be administered as an oral dose daily. The dose planned in this study is 3 g per day (3 500mg capsules to be taken twice daily). The dosing decision is based on the mechanism of action, the pharmacology in non-human studies (the drug has extensive pre-clinical pharmacokinetic and pharmacodynamic testing) and human data for completed studies across a number of therapeutic indications (see references in toxicity section above). The proposed dose of 3 g per day has been used in a number of human trials reporting side effects ranging from absence of any side effects to mild side effects; otherwise, the drug has been well tolerated. Mahdavi et al. conducted a double-blind placebocontrolled randomized clinical trial to determine the effects of NS oil combined with a calorie-restricted diet on systemic inflammatory biomarkers in obese women. 90 volunteer obese women were enrolled. The intervention group received 3 g/day NS oil soft gel capsules (one capsule, three times a day, 30 minutes before each main meal), and the placebo group received similar amounts of sunflower oil as a placebo for eight weeks. Subjects reported no side effects during the intervention except mild gastrointestinal problems [81]. In a study by Bamosa et al., patients with type 2 diabetes mellitus were randomly divided into 3 groups to receive Nigella Sativa seed extracts at 1 gm, 2 gms and 3 gms per day respectively for 12 weeks. In the study, generally, the three doses of Nigella sativa were well tolerated with only three patients who experienced a mild epigastric discomfort that settled down after taking the capsules post meals [68]. In a study by Datau et al. performed on 39 centrally obese men assigned to receive NS seeds (3 g/day for 3 months) or placebo, subjects reported subjective complaints related to central obesity (body ache, weakness, sleeplessness, belching, decreased libido). All subjective complains reported by subjects in the treatment group disappeared in the first week of the study, but they all still persisted in the control group through the end of the study. [65].

Enteric coated formulation

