8.3 ADVERSE EVENTS AND SERIOUS ADVERSE EVENTS

8.3.1 DEFINITION OF ADVERSE EVENTS (AE)

Adverse event is defined as any untoward medical occurrence associated with the use of an intervention in humans, whether or not considered intervention-related (21 CFR 312.32 (a)).

For this study, adverse events will be captured from the time of informed consent until 7 days after last dose of investigational product (30 days after last dose for SAEs)

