8.3.4 TIME PERIOD AND FREQUENCY FOR EVENT ASSESSMENT AND FOLLOW-UP

The occurrence of an adverse event (AE) or serious adverse event (SAE) may come to the attention of study personnel during study visits and interviews of a study participant presenting for medical care, or upon review by a study monitor.

All AEs including local and systemic reactions not meeting the criteria for SAEs will be captured on the appropriate electronic case report form (eCRF). Information to be collected includes event description, time of onset, clinician's assessment of severity, relationship to study product (assessed only by those with the training and authority to make a diagnosis), and time of resolution/stabilization of the event. All AEs occurring while on study must be documented appropriately regardless of relationship. All AEs will be followed to adequate resolution.

Any medical condition that is present at the time that the participant is screened will be considered as baseline medical history and not reported as an AE. However, if the study participant's condition deteriorates at any time during the study, it will be recorded as a new AE.

Changes in the severity of an AE will be documented to allow an assessment of the duration of the event at each level of severity to be performed. AEs characterized as intermittent require documentation of onset, severity, and duration of each episode.

The principal investigator or designee will record all reportable events with start dates occurring any time after informed consent is obtained until 7 (for non-serious AEs) or 30 days (for SAEs) after the last dose of study drug. At each study visit, the investigator will inquire about the occurrence of AE/SAEs since the last visit. Events will be followed for outcome information until resolution or stabilization. A final follow-up phone call will be performed at Day 45 in order to assess status of any ongoing AEs or SAEs. Any AEs that are considered unresolved at Day 45 will be followed clinically by the investigator until resolution or stabilization.

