## 4.2 Safety Endpoints

Number of overall adverse events, related adverse reactions, and hospitalizations reported in participants taking 3 g TQ Formula (500 mg per capsule, 3 capsules BID) versus participants

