Primary Estimand-2 for the safety objective is the difference of frequencies of Adverse Events and Serious Adverse Events between participants taking 3 g TQ Formula (500 mg per capsule, 3 capsules BID) and participants taking placebo regardless of whether or not they actually receive their assigned therapy (ITT) and assuming that their hospitalization and treatment discontinuation rates will be similar. The above mentioned intercurrent events are also applicable for this safety estimand. Therefore, hospitalization-free, while-on-study and per-protocol treatment versions of the above estimand will also be considered within each population definitions above.

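### New or worsened Covid-19 symptoms count as adverse events, and the SAP's safety estimand does not separate them from other events, so a drug-caused excess can be offset or diluted in that comparison.

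*Protocol*

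**What the plan says.** **Recording.** Protocol 8.3.1 defines an AE as "any untoward medical occurrence associated with the use of an intervention in humans, whether or not considered intervention-related". Section 8.3.4 sets the boundary at screening: "Any medical condition that is present at the time that the participant is screened will be considered as baseline medical history", so it falls outside the AE count. Later worsening is treated differently: "if the study participant's condition deteriorates at any time during the study, it will be recorded as a new AE". Section 8.3.5 adds newly emerging signs or symptoms and pre-existing conditions that worsen. For physical examinations, section 4.1 says "New or worsened clinically significant abnormalities should be recorded as adverse events". None of these rules excepts Covid-19. The term Disease-Related Event occurs only in the two abbreviation lists, and Protocol 8.3.8 marks events of special interest as not applicable.

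**Analysis.** SAP 3.6 makes safety a primary objective; the Protocol has it as secondary. Primary Estimand-2 in SAP 5.3.2 is "the difference of frequencies of Adverse Events and Serious Adverse Events between participants" on TQ Formula and on placebo. The endpoint in SAP 4.2 is wider: "Number of overall adverse events, related adverse reactions, and hospitalizations reported in participants". Protocol 9.4.3 also plans:
- tables by grade and attribution;
- a Toxicity category for AEs at least possibly attributed to therapy;
- Fisher's exact tests on any AE or a set of AEs, when frequencies allow;
- the same comparisons for toxicities of interest.

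SAP 5.3.6 summarises AEs by severity and relationship to study drug. Neither document plans a split of Covid-19 from other AEs.

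**The concern.** Inclusion requires active, symptomatic Covid-19, and the hypothesised benefit is faster relief of symptoms. Some of the events counted under Estimand-2 will be new or worsening symptoms of the disease being treated. Benefit on those symptoms lowers the count used to judge harm. Without such benefit, disease events common to both arms raise both rates and shrink the visible effect of the drug's own AEs.

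The overlap is greatest where product effects are expected. Nausea, stomach ache, vomiting and diarrhoea are items of the Modified FLU-PRO Plus (Protocol Appendix 2). Protocol 2.2.2 reports nausea and bloating with the product, and for one study at 3 g/day Protocol 4.3 says "Subjects reported no side effects during the intervention except mild gastrointestinal problems". At stake is the fifth secondary hypothesis in Protocol 9.1, that the AE and SAE profiles are acceptable compared with placebo. An apparently balanced overall AE rate could be read as support for it.

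**Working it through.** The plan states no AE rate, so there is no figure of its own to reproduce. The check is an illustration of the mechanism.

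**Inputs from the documents.** 26 to 30 participants per arm (SAP 3.2); two-sided 0.05 (Protocol 9.4.1); Fisher's exact test on the percentage of patients with an AE (Protocol 9.4.3).

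**Assumed inputs.** Covid-19 AE risk: placebo 20% to 50%, drug 10% to 40%. Other AE risk: placebo 5%, drug 25% or 40%. The two kinds of AE are taken as independent within a participant.

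**Formula.** Any-AE risk = 1 − (1 − c)(1 − x), where c is the Covid-19 AE risk and x the other-AE risk. For c = 40% against 20% and x = 5% against 25%:
- placebo: 1 − 0.60 × 0.95 = 43.0%;
- drug: 1 − 0.80 × 0.75 = 40.0%;
- difference: −3.0 points, against +20 points for other AEs alone.

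Power below is the exact probability that the Fisher test is significant in the direction of harm, at 30 per arm.

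| Covid-19 AEs, placebo / drug | Other AEs, placebo / drug | Any AE, placebo / drug | Difference (points) | Power, all AEs | Power, other AEs alone |
|---|---|---|---|---|---|
| 20% / 10% | 5% / 25% | 24.0% / 32.5% | +8.5 | 6.7% | 43.6% |
| 40% / 40% | 5% / 25% | 43.0% / 55.0% | +12.0 | 10.1% | 43.6% |
| 40% / 20% | 5% / 25% | 43.0% / 40.0% | −3.0 | 0.7% | 43.6% |
| 50% / 30% | 5% / 25% | 52.5% / 47.5% | −5.0 | 0.5% | 43.6% |
| 20% / 10% | 5% / 40% | 24.0% / 46.0% | +22.0 | 33.0% | 89.3% |
| 40% / 40% | 5% / 40% | 43.0% / 64.0% | +21.0 | 28.3% | 89.3% |
| 40% / 20% | 5% / 40% | 43.0% / 52.0% | +9.0 | 6.5% | 89.3% |
| 50% / 30% | 5% / 40% | 52.5% / 58.0% | +5.5 | 3.7% | 89.3% |

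At 26 per arm the third row gives 0.8% and 39.7%. The second row shows that dilution needs no drug benefit.

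**Does attribution remove the problem?** Protocol 8.3.3.2 has no category between Possibly Related and Not Related. Possibly Related admits events for which underlying disease is a plausible explanation. Not Related demands a documented, definitive alternative cause. An ambiguous Covid-19 symptom can therefore be classed as possibly related, and so counted as Toxicity. Suppose a fraction q of Covid-19 AEs is called related, and all other AEs are. Related-AE risk is then 1 − (1 − qc)(1 − x). For c = 40% / 20% and x = 5% / 25%:

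| q | Related AEs, placebo / drug | Difference (points) | Power |
|---|---|---|---|
| 0 | 5.0% / 25.0% | +20.0 | 43.6% |
| 0.25 | 14.5% / 28.75% | +14.3 | 17.6% |
| 0.5 | 24.0% / 32.5% | +8.5 | 6.7% |
| 1 | 43.0% / 40.0% | −3.0 | 0.7% |

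**The case against.** A reader might infer that the plan only ever counts all AEs together. It does not. Related reactions are part of the endpoint, grade and attribution tables are planned, and Protocol 9.4.3 compares toxicities of interest between arms. The point is confined to Estimand-2, with the other summaries as a partial safeguard.

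A reader might also infer that any drug that shortens illness would look safe. The documents do not support that. Under Protocol 8.3.4 a symptom present at screening that persists without worsening is never an AE, so ending it sooner removes none. The offset needs the drug to prevent new or worsening symptoms. Its size rests on rates the documents do not give: with other AEs at 5% against 40%, the excess keeps its sign in every scenario shown.

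The sentence quoted from Protocol 4.1 concerns examination findings and does not name Covid-19 symptoms; the argument rests on 8.3.1, 8.3.4 and 8.3.5.

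Four further objections have weight:
- Attribution is made blind, so misattribution should not favour an arm. It still dilutes, as the second table shows.
- No decision rule uses the all-AE contrast. The only safety halting rule (Protocol 9.4.4, SAP 7.6) counts attributable, unresolved Grade 3+ events.
- An all-AE comparison is a valid estimate of the net randomised effect. That is a reason to keep it.
- A term list taken from the whole questionnaire could hide harm. Loss of appetite and fatigue are questionnaire items, and Protocol 8.5 names anorexia and fatigue among early symptoms of drug-induced liver injury. The fix has to guard against this.

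**Conclusion.** The concern holds for the overall AE comparison. New or worsened Covid-19 symptoms are AEs, and Estimand-2 does not separate them, so a benefit on illness can offset a drug-caused excess and shared disease events can dilute it. Under the assumed rates, a true 20-point excess appears as anything from −5 to +12 points, and a 35-point excess as +5.5 to +22. These ranges assume independence and the rates listed; they are not predictions for this trial. The attribution, grade and toxicity summaries reduce the problem without removing it.

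This is an inexpensive improvement to how safety is presented and does not invalidate the safety analysis. The SAP's listing of safety as a primary objective adds to its weight. The split will not make the trial well powered for harm: even separated, 5% against 25% at 30 per arm has 43.6% power.

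**What to change.** In SAP 5.3.2 (Primary Estimand-2) and 5.3.6, keep the all-AE and all-SAE comparison and add beside it the arm difference in AEs excluding Covid-19 symptoms or progression. Define the excluded events by a term list fixed before any unblinding, including the statistician's unblinding for the preliminary efficacy report in SAP 7.7.

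Keep terms that overlap with reported product effects or with the liver-injury symptoms in Protocol 8.5 in the non-Covid group: nausea, vomiting, stomach ache, diarrhoea, loss of appetite and fatigue. Also show these separately by arm. The non-Covid group will then still contain some disease events, and the separate display lets the reader see how much of any difference they carry.

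AE recording rules stay unchanged and no new data are needed. The cost is SAP wording, one term list, one extra table and some blinded judgement in fixing the list.

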4.2 SCIENTIFIC RATIONALE FOR STUDY DESIGN

Blackseed oil has been shown to possess anti-inflammatory properties, and anti-corona virus properties, based on our extensive literature and our pre-clinical studies that showed its activity in blocking viral entry. See sections 2.2 and 2.3 for details.

This study design (study drug versus placebo) was chosen as there are currently no known outpatient treatments for Covid-19. Participants can maintain their regular standard of care, irrespective of treatment allocation, and are allowed to take any additional vitamins or supplements.

The randomization of participants will allow researchers to determine any significant differences between treatment groups. Participants will be blinded to their treatment, in order to remove any reporting bias on the patient reported outcome questionnaire.

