5.2 EXCLUSION CRITERIA

An individual who meets any of the following criteria will be excluded from participation in this study:

1. Current or recent (within 4 weeks) treatment with any corticosteroids; however, high-dose inhaled steroids, which are used to treat acute or chronic bronchial inflammation, will be permitted
2. Current or recent (within 4 weeks) treatment with any antivirals
3. Room air oxygen saturation (SaO_2) $< 94\%$ at screen
4. Walking oximetry $< 90\%$ or participant unable to complete 6-minute walking oximetry test at screen
5. Severe Covid-19 symptoms (severe per FDA classification – see appendix 3)
6. Requires immediate admission to hospital for any reason
7. Pregnancy or lactation
8. Known allergic reactions to components of black seed oil, or thymoquinone
9. Treatment with another investigational drug or other investigational intervention within 2 weeks of study start and throughout study duration.
10. Significant hepatic disease ($\text{ALT}/\text{AST} > 4$ times the ULN); any laboratory parameter ≥ 4 times the ULN
11. History of severe chronic kidney disease or history of liver disease

12. Patients with inflammatory bowel disease (such as Crohn's) that could affect the intestinal absorption of TQ Formula enteric coated capsules.
13. Known HIV or Hepatitis C infection
14. Influenza diagnosis (confirmed by testing) during screening or within prior 14 days
15. Any uncontrolled condition(s) or diagnosis, both physical or psychological, or physical exam finding that precludes participation, as per investigator

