5.3 LIFESTYLE CONSIDERATIONS

It is recommended that doses be taken with food, approximately 12 hours apart. Participants may continue with their normal standard of care, including any supplements or vitamins.

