6 STUDY INTERVENTION

6.1 STUDY INTERVENTION(S) ADMINISTRATION

6.1.1 STUDY INTERVENTION DESCRIPTION

The study intervention is TQ Formula capsules, 500 mg per capsule. The control product is placebo capsules, identical in appearance to TQ Formula capsules but with no active ingredients.

Black seed oil is currently available as a food supplement, with 500 mg capsules being sold over the counter. For the purposes of this trial, both TQ Formula and placebo capsules will be manufactured as over-encapsulated capsules. A specific batch and lot will be produced, with appropriate stability testing.

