6.2.2 FORMULATION, APPEARANCE, PACKAGING, AND LABELING

The investigational drug consists of 500 mg of black seed oil per capsule. Placebo consists of similar oil without active ingredient. Investigational drug will be undistinguishable from placebo; the appearance of the capsules and all packaging will be identical. Investigational product will be packaged as 500 mg/placebo capsules; each participant will receive a total of 84 capsules in order to take 6 capsules per day for the 14-day study treatment period. Investigational product will be labelled per CFR regulations.

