6.5 CONCOMITANT AND PROHIBITED THERAPY

For this protocol, a prescription medication is defined as a medication that can be prescribed only by a properly authorized/licensed clinician. Medications to be reported in the Electronic Case Report Form (eCRF) are concomitant prescription medications, over-the-counter medications and supplements.

Concomitant medication usage will be collected at screening and throughout the course of the study at each study visit. Any medication currently being taken at the time of screening will be recorded at the screening visit. Any changes in concomitant medication usage will be documented throughout the course of the study during study visits.

All standard of care medication to treat Covid-19 is allowed per investigator discretion.

Prohibited Medications

All standard of care medication is allowed during the course of the clinical trial. The use of any drugs approved to treat severe Covid-19 requiring hospitalization, such as: corticosteroids, antivirals, Hydroxychloroquine is prohibited for entry into the study. The use of these medications is considered inpatient regimen for severe Covid-19, and these patients are excluded from this trial. If any participant requires these medications due to worsening of Covid-19 symptoms, study treatment will be stopped and participant will continue to be followed for safety (See Appendix 4).

Investigators should carefully assess patients who are currently being treated with any drugs that are metabolized by CYP2C9 due to potential for interaction with Thymoquinone (See Appendix 5).

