9.4 STATISTICAL ANALYSES

9.4.1 GENERAL APPROACH

Categorical variables will be presented as frequencies and percentages with column and row percentages in 2x2 or Rx C tables as appropriate. Association between two nominal variables will be investigated using Chi-Square tests and/or Fisher's Exact test as needed. Cochran Armitage trend-test may be included among the possible tests to investigate the possible trend between one ordinal factor and one binary factor. Association between two ordinal variables may be investigated through Non-zero Correlation test. Continuous variables will be presented as mean and standard deviation as well as five-number summary (minimum, first quartile, median, third quartile, and maximum). Range and inter-quartile range may also be explicitly provided as needed. Distribution of a continuous variable among the levels of a binary or polynomial factor will be investigated graphically through boxplots and through Wilcoxon-MannWhitney test and/or Kruskal Wallis tests. Association between two continuous variables will be described through scatter plots and Pearson's and Spearman's correlation coefficients as appropriate. When needed, normality assumption of a given continuous variable will be tested using Shapiro-Wilk Normality test. The details of the statistical models addressing each and every primary, secondary, and exploratory objectives along with primary predictors and control variables will be provided in a corresponding Statistical Analysis Plan (SAP). In this protocol document, a general analysis and statistical testing approach will be provided, and the details will be left for the study SAP.

In all comparisons and tests, a two-sided p-value will be used and a Type-1 error rate of 0.05 will be used to indicate significance. No multiplicity correction will be employed for statistical tests addressing the two primary objectives. Similarly, no multiplicity correction will be employed for statistical tests addressing the secondary and exploratory objectives as the results from these objectives must be considered within the hypotheses generating context.

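### The permission to take any supplement makes no exception for over-the-counter black seed oil, so placebo participants may take the test substance without a deviation, which could dilute the contrast

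*Protocol*

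**What the plan says.** Protocol section 4.2 lets participants keep their standard of care whichever arm they are in, and adds that they "are allowed to take any additional vitamins or supplements". Section 5.3 repeats this: "Participants may continue with their normal standard of care, including any supplements or vitamins". Inclusion criterion 9 asks participants to agree to section 5.3, so the permission is part of what they sign up to.

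Section 6.1.1 states: "Black seed oil is currently available as a food supplement, with 500 mg capsules being sold over the counter". Section 6.2.2 states: "The investigational drug consists of 500 mg of black seed oil per capsule". Substance and capsule strength are therefore the same. The study capsules are nevertheless over-encapsulated from a specific batch (6.1.1) and enteric-coated (4.3).

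The places where an exception might be expected do not contain one:

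- **Exclusion criteria (Protocol 5.2, SAP 3.3.2).** Black seed oil and thymoquinone appear only as allergens. The nearest criterion is "Treatment with another investigational drug or other investigational intervention within 2 weeks of study start and throughout study duration". It concerns investigational products and does not clearly reach a food supplement that other sections expressly allow.
- **Prohibited therapy (Protocol 6.5, Appendix 4).** The restriction is tied to drugs for severe Covid-19. The appendix calls itself non-exhaustive, but everything it lists is of that kind.
- **Compliance (Protocol 6.4).** Only study product is checked.
- **Intercurrent events (SAP 5.3.2).** Hospitalization and treatment discontinuation are the only ones named.

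Two safeguards exist. Section 6.5 requires recording of "concomitant prescription medications, over-the-counter medications and supplements", and section 4.1 says the same for vitamins and supplements at screening. SAP section 5.3.4 describes plasma metabolite concentrations in each arm and compares the arms on Days 1, 7 and 14.

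**The concern.** Read together, these sections let a placebo participant buy and take the substance under test while remaining fully within protocol. Current users are not excluded either. Participants are told the purpose of the study at consent (section 4.1), and the product needs no prescription, so such use is plausible.

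If the product works, use in the placebo arm moves that arm toward the active arm under the intent-to-treat analysis and costs power. The adverse-event comparison, which SAP section 3.6 lists as a second primary objective, would be blurred in the same direction, and there a shift toward no difference is not conservative. Because permitted use is not a violation, users would also stay in the per-protocol set, so no planned analysis separates them.

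**Working it through.** **Inputs.** Protocol 9.2 gives a placebo median of 16 days, a difference of 10 days (so an active median of 16 − 10 = 6), 20 per arm, power 81.5%, 21-day follow-up, and about 20% attrition leading to 26 per arm. Protocol 9.4.1 states that "a two-sided p-value will be used and a Type-1 error rate of 0.05 will be used to indicate significance". Exponential times are my assumption, and the 21 days are counted from the same origin as the medians. The share c of placebo participants using non-study black seed oil is also an assumption, because the documents give no figure.

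**The plan's own figure.** The rate ratio is 16/6 = 2.667. Freedman's formula with all 40 participants counted as events gives Φ(√40 × 1.667/3.667 − 1.96) = Φ(0.915) = 82.0%, close to the stated 81.5%. For attrition, 20/(1 − 0.2) = 25, against 26 planned.

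**Allowing for 21-day follow-up.** The chance of responding by Day 21 is 1 − 0.5^(21/16) = 0.597 on placebo and 1 − 0.5^(21/6) = 0.912 on active. Expected events are 20 × (0.597 + 0.912) = 30.2. Schoenfeld's formula gives Φ(½√30.2 × ln 2.667 − 1.96) = Φ(0.734) = 76.9%. This is the baseline for what follows.

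**Adding non-study use.** Each user in the placebo arm is given the full active-arm distribution from the start. The placebo median m then solves (1 − c) × 0.5^(m/16) + c × 0.5^(m/6) = 0.5. For c = 20%, m = 13.0, since 0.8 × 0.569 + 0.2 × 0.223 = 0.500. The diluted rate ratio is taken as m/6. Expected events are 20 × [(1 − c) × 0.597 + c × 0.912 + 0.912]. Power is Φ(½√events × ln(m/6) − 1.96).

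| Use in placebo arm (assumed) | Placebo median, days | Difference, days | Rate ratio | Events | Power, formula | Power, simulated log-rank |
|---|---|---|---|---|---|---|
| 0% | 16.00 | 10.0 | 2.667 | 30.2 | 76.9% | 76–77% |
| 5% | 15.22 | 9.2 | 2.536 | 30.5 | 72.9% | 72–74% |
| 10% | 14.45 | 8.5 | 2.409 | 30.8 | 68.4% | 68–69% |
| 20% | 13.00 | 7.0 | 2.167 | 31.4 | 58.2% | 58–60% |

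The mixture does not have strictly proportional hazards, so the formula is approximate. The last column gives the range over repeated simulations of the log-rank test and agrees with it.

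**Sensitivity to method.** With the Freedman calculation that reproduces the stated power, the path is 82.0%, 78.5%, 74.3% and 64.5%.

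**Sensitivity to effect in users.** Simulated at 26 per arm with no dropout, power starts at 86–88% and falls to 79–80% at 10% use and 69–71% at 20% use when users get the full effect. If users get half the log-hazard benefit, it falls only to about 83–84% and 79–80%. The 26-per-arm figures are optimistic, because 26 was chosen to absorb attrition.

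**Scale.** With 20 per arm, two placebo users are already 2/20 = 10%.

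**The case against.** The strongest reply is that background therapy open equally to both arms is compatible with a placebo control, so nothing here is a contradiction. That stands: the defect is a missing exception. Any bias in the efficacy comparison is toward no difference. If the product does nothing, taking it changes nothing, so the Type-1 error is not inflated.

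Second, the safeguards are real. Supplement use is already documented at screening and reviewed at visits, major violations are to be identified before unblinding, and the metabolite comparison could reveal placebo-arm exposure. What remains is that recording does not prevent use, that expressly permitted use has no basis for being called a violation, and that the metabolite check is exploratory. It is also uncertain whether placebo samples will be assayed: Protocol section 3 and SAP 4.1.3 confine the thymoquinone endpoint to patients treated with TQ Formula, while SAP 5.3.4 compares arms.

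Third, some stronger inferences are not supported. A reader might conclude that the contrast *is* diluted, but no use rate is given. One might say that placebo participants can take the study drug itself, but the documents show the same substance and strength, not the over-encapsulated, enteric-coated study form. One might add that prior use distorts the baseline, but randomization balances prior use in expectation. Nor does section 9.2 state that its 16-day median assumes no exposure; it takes the figure from a CDC report on outpatients.

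Finally, SAP section 2.2 cites protocol Version 6.0, and its exclusions differ in places from the protocol reviewed here (for example, it adds CYP2C9 substrates). The SAP does not repeat the supplement permission, so the wording should be checked in the version in force.

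**Conclusion.** The concern holds as a gap that could dilute the contrast; it does not show that dilution occurs. As written, a placebo participant may take non-study black seed oil without a deviation, and no planned analysis would identify or account for it. The direction is clear if the product has any effect. The size is not known, because the use rate is not known.

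Under the planning medians, exponential times, 21-day censoring and 20 per arm, power of about 77% would fall to no lower than about 72–73%, 68% and 58% at 5%, 10% and 20% use. These losses are upper bounds for each rate: they give every user the full effect of the 3 g/day regimen from the start, and lower doses, later starts or a weaker product would cost less. The gap should be closed, because the study is small and the remedy cheap, but it does not invalidate the design.

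**What to change.** In the protocol, reconcile the supplement wording in sections 4.2 and 5.3 with the placebo control by excepting the test substance itself, that is, non-study black seed, Nigella sativa and thymoquinone products, in both arms. Since inclusion criterion 9 already refers to section 5.3, a sentence there reaches eligibility. How this applies to people already taking such products is for the sponsor to decide. Add a named prompt for these products to the existing concomitant-medication review.

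In the SAP, class non-study use as a major deviation for the per-protocol set, tabulate it by arm, and use the metabolite data already planned as a check. For that, state that placebo samples are assayed, and align SAP 4.1.3 with 5.3.4. Sampling on three days can miss use in between, so the check supplements the prompt and does not replace it.

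The cost is one sentence in each of two protocol sections, one eCRF prompt and a few lines of SAP text. Assaying placebo samples adds laboratory work only if it is not already intended. The downside is that a few current users may decline or be ineligible.
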